2.4. Trial Day

Trial endpoints will be reported within analysis windows or analysis intervals based upon the actual date of the assessment. Assignment of results to these time points is based upon the trial day. Trial day is defined as:

$$\text{Trial day} = \text{date of assessment} - \text{date of treatment}$$

Analysis Windows used to report non-diary endpoints are outlined in [Table 3](#).

Table 3: Analysis Windows

Visit	Range	Target Day	If more than one which one is used for analyses
Screening	< Day 0		First value
Day 0	Day 0 to Day 9	Day 0	Closest to Target Day
Week 2	Day 10 to Day 21	Day 14	Closest to Target Day
Week 4	Day 22 to Day 42	Day 28	Closest to Target Day
Week 8	Day 43 to Day 70	Day 56	Closest to Target Day
Week 12	Day 71 to Day 98	Day 84	Closest to Target Day
Week 16	Day 99 to Day 126	Day 112	Closest to Target Day
Week 20	Day 127 to Day 154	Day 140	Closest to Target Day
Week 24	Day 155 to Day 203	Day 168	Closest to Target Day
Week 32	> Day 204	Day 224	Closest to Target Day

Note: If two observations exist with same distance to target day, use first observation.

For the eDiary data used to produce the migraine and headache endpoints the intervals specified in Table 4 will be used to collapse the daily data into 4, 12, and 24 week intervals. For these data baseline is defined as the 28 days starting on the day of the first diary entry.

Table 4: eDiary Headache/Migraine Endpoint Analysis Intervals

Diary Weeks	Trial Time	Comments	Endpoints
Baseline	The 28 days starting from the first eDiary entry		All eDiary related endpoints
1-4	Days: 0-27	Day 0 = First day of treatment	All eDiary related endpoints
5-8	Days: 28-55		All eDiary related endpoints
9-12	Days: 56-83		All eDiary related endpoints
1-12	Weeks 1-4, 5-8, and 9-12	Average of the 4 week intervals after imputation methods are applied	All Primary and Secondary eDiary related endpoints
13-16	Days: 84-111		All eDiary related endpoints
17-20	Days: 112-139		All eDiary related endpoints
21-24	Days: 140-167		All eDiary related endpoints
13-24	Weeks 13-16, 17-20 and 21-24	Average of the 4 week intervals after imputation methods are applied	All Primary and Secondary eDiary related endpoints
1-24	Weeks 1-4, 5-8, 9-12, 13-16, 17-20 and 21-24	Average of the 4 week intervals after imputation methods are applied	All Primary and Secondary eDiary related endpoints

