⁸ Vital signs measured pre-dose and within 2 hours post-dose on Days 0 and Week 12.

⁹ C-SSRS "Baseline/Screening Version" should be used at screening, and C-SSRS "Since Last Visit Version" should be used on Day 0 (pre-randomization), Weeks 2,4, 8, 12 (pre-dose), 16, 20, 24, and 32 or ET.

¹⁰ Inclusion/exclusion criteria review, C-SSRS, and urine pregnancy test must be done prior to dosing on Day 0. C-SSRS and urine pregnancy test must be done prior to dosing at Week 12.

¹¹ Conduct ECG pre-dose, and within 2 hours post dose on Day 0 and Week 12.

¹² Blood draws obtained pre-dose on dosing days (within 1 hour before dosing). On Day 0, draw additional PK immediately post dose (within 15 minutes of end of infusion). Subjects who test positive for anti-ALD403 antibodies at the last study visit will be asked to provide up to 2 additional blood samples for immunogenicity testing at 3 month intervals for up to 6 months.

¹³ Subjects must be monitored for at least 2 hours after the dosing completion to assess for the occurrence of adverse events. Subjects will be requested to stay longer than 2 hours after dosing should the investigator determine this is clinically warranted (e.g., subjects should be observed until all AEs are resolved or clinically stable).

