3.6.4.3. Electrocardiogram Results

The observed data at baseline and change from baseline for each measurement day will be summarized with descriptive statistics by treatment group.

The overall ECG assessment based upon PI assessment will be summarized including post treatment ECGs determined to be abnormal clinically significant.

The absolute QTcF values provided by the core lab will be analyzed as a categorical variable. Each QTcF value in a given patient will be grouped into 4 categories:

- QTcF interval < 450 msec
- QTcF interval 450 - 480 msec
- QTcF interval > 480 - 500 msec
- QTcF interval > 500 msec

The changes in QTcF measures will also be analyzed as categorical variables. The change in QTcF in a given patient will be grouped into 2 categories:

- QTcF interval increases from baseline > 30 msec
- QTcF interval increases from baseline > 60 msec

The overall ECG assessment will be summarized along with a summary of how many subject developed a post treatment abnormal clinically significant result. Denominators for percentages will use the number of assessments available at each visit.

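### Read literally, the Table 3 tie rule leaves same-day post-dose vital signs and ECGs out of the by-day safety summaries, and post-dose vital signs have no other dedicated summary

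*SAP*

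**What the plan says.** **Window rule (SAP 2.4, Table 3).** Assignment is by date: "Trial endpoints will be reported within analysis windows or analysis intervals based upon the actual date of the assessment". Trial day is the assessment date minus the treatment date, with no clock time. The scope is general: "Analysis Windows used to report non-diary endpoints are outlined in" Table 3. Each post-treatment visit has one row, and if a window holds several values the one nearest the target day is used. The note under the table settles ties: "If two observations exist with same distance to target day, use first observation".

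**Collection on dosing days (Protocol 2, footnotes 8 and 11).** "Vital signs measured pre-dose and within 2 hours post-dose on Days 0 and Week 12" and "Conduct ECG pre-dose, and within 2 hours post dose on Day 0 and Week 12". The ECG footnote in SAP Table 1 agrees with the protocol. The SAP's vital-sign footnote gives 4 hours after dosing instead of 2.

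**Summaries.** SAP 3.6.4.1 (vital signs) and the first paragraph of SAP 3.6.4.3 (ECG) plan baseline values and change from baseline by measurement day. Neither names a post-dose time point. For vital signs the only other planned output is a plot of averages over time. For ECGs, SAP 3.6.4.3 also says "Each QTcF value in a given patient will be grouped into 4 categories" and summarises post-treatment ECGs judged abnormal and clinically significant.

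**Baseline (SAP 3.2).** For non-diary variables it is the last valid value before dosing, generally from Day 0.

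**Late windows (Table 3).** Week 24 is "Day 155 to Day 203". Week 32 is defined as strictly later than Day 204.

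**The concern.** A pre-dose and a post-dose reading taken on the same visit have the same trial day, so they are equally far from any target day. This happens by design at both dosing visits. The tie note then selects the earlier reading, which is the pre-dose one. A programmer who follows Table 3 as written would produce by-day tables that look complete but carry no post-infusion information on dosing days.

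Vital signs and ECGs are named safety endpoints, and the post-dose readings are their scheduled measurements closest to the infusion. At stake is the descriptive picture of average post-infusion change, above all in blood pressure and pulse.

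**Working it through.** The plan states no figure to reproduce. The check applies Table 3 literally to the visit schedule.

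**1. Day 0.** The window is Days 0 to 9 with target Day 0. The pre-dose and post-dose readings are both at distance |0 − 0| = 0. They tie, and the pre-dose reading is kept. By SAP 3.2 that reading is generally the baseline itself, so the Day 0 change is baseline − baseline = 0.

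**2. Week 12.** The window is "Day 71 to Day 98" with target Day 84. The visit is allowed at Day 84 ± 3, that is Days 81 to 87.

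| Trial day | 81 | 82 | 83 | 84 | 85 | 86 | 87 |
|---|---|---|---|---|---|---|---|
| Distance, pre-dose | 3 | 2 | 1 | 0 | 1 | 2 | 3 |
| Distance, post-dose | 3 | 2 | 1 | 0 | 1 | 2 | 3 |
| Kept | pre | pre | pre | pre | pre | pre | pre |

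All seven permitted days give a tie, and the pre-dose reading is kept each time. A post-dose reading would be used only if its pre-dose partner were missing, and the visit row would then mix the two kinds of reading.

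**3. Number of readings.** 1050 subjects × 2 dosing days = 2100 post-dose sets for each of vital signs and ECG. On ALD403: 2 arms × 350 × 2 = 1400 for each. These are ceilings, because they assume that every subject attends both dosing visits and has both readings.

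**4. Where a post-dose reading can still appear.**

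| Output | Post-dose vital signs | Post-dose ECG |
|---|---|---|
| Descriptive summary by day | left out under the literal rule | left out under the literal rule |
| Absolute QTcF categories | not applicable | retained (each value is categorised) |
| Counts of clinically significant ECGs | not applicable | retained |
| Adverse-event and special-interest tables | only if reported as an event | only if reported as an event |

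The categories for QTcF increase from baseline do not say whether every value is used.

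**5. Window boundaries.** Each window through Week 24 starts on the day after the previous one ends (9/10, 21/22, 42/43, 70/71, 98/99, 126/127, 154/155). Week 24 ends on Day 203 and Week 32 begins on Day 205. Day 204 is therefore the only gap, and there are no overlaps. On-schedule Week 24 visits fall on Days 168 to 175 and Week 32 visits on Days 217 to 231. Only early-termination, unscheduled or out-of-window assessments could land on Day 204.

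**The case against.** The strongest reply is that the tie note has an ordinary purpose, to choose between repeat assessments on either side of a target day such as Days 82 and 86, and was never meant to make two scheduled time points compete. The drug-concentration text supports this. SAP 2.2.3 and 3.5 list the sample taken immediately after the Day 0 infusion as its own time point, yet under a literal Table 3 that sample would also lose to its pre-dose partner. So Table 3 cannot be meant literally for every endpoint. That stands, and it makes a sensible programming departure plausible. But the SAP supplies the separate time point only for drug concentrations. For vital signs and ECGs nothing overrides the written rule.

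A reader might infer that the plan excludes 2100 post-infusion ECGs and vital-sign sets from analysis altogether, or that an acute effect of the infusion could not be seen. The documents do not support that:

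- The readings are still collected.
- SAP 3.6.4.3 keeps post-dose ECGs in the absolute QTcF categories and in the counts of clinically significant ECGs.
- Subjects are observed for at least 2 hours after dosing, and clinically significant findings are recorded as adverse events (Protocol 9.3 and 11.1.2).
- SAP 3.6.2.1 tabulates cardiovascular events of special interest, including blood pressure, heart rate and QT terms.

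These outputs capture events and threshold crossings. They do not replace a summary of average post-infusion vital signs.

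It is also fair to say that these tables are descriptive. No hypothesis test, power figure or efficacy result depends on them.

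**Conclusion.** The point holds for the descriptive by-day summaries. Under the literal rule, post-dose vital signs and ECGs on Day 0 and at Week 12 are left out wherever the pre-dose reading exists, and Day 0 change from baseline is generally zero. The material loss is post-infusion vital signs, because SAP 3.6.4.1 gives them no other dedicated summary. For ECGs the loss is limited to the descriptive means. How far the tables would really be affected depends on whether the programmer follows Table 3 as written, which the SAP leaves to chance.

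This is more than missing detail, since a stated rule selects the wrong reading for the purpose. It should be corrected, but it does not threaten the trial's conclusions on efficacy.

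The Day 204 gap is a minor boundary slip that touches few records. The 2-hour and 4-hour limits for post-dose vital signs are a separate contradiction about data collection. It lends no weight to the tie-rule point, but the two passages must be reconciled.

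**What to change.** Amend the SAP as follows:

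1. **SAP 2.4.** State that for vital signs and ECGs the window and tie rules apply within nominal time point (pre-dose, post-dose) on Day 0 and at Week 12.
2. **SAP 3.6.4.1 and 3.6.4.3, Day 0.** Summarise post-dose as change from the pre-dose baseline. A pre-dose change row is not needed, because it would generally be zero.
3. **Same sections, Week 12.** Summarise pre-dose and post-dose as change from baseline, and also post-dose as change from the same-day Week 12 pre-dose value. Only the last isolates an acute effect, because change from Day 0 also contains 12 weeks of treatment and drift.
4. **SAP 3.6.4.3.** State that the QTcF categories, both absolute and change, use all values.
5. **Table 3.** Let the Week 32 window start on Day 204 (≥ instead of >). This leaves no gap and no overlap.
6. **Protocol 2 and SAP Table 1, footnote 8.** Reconcile the two limits for post-dose vital signs.

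The cost is SAP wording and a few extra rows in the vital-sign and ECG tables. Items 1 to 5 need no new data, and nothing here affects power or the type I error rate. The change is best made before the unblinding that SAP 1.4 plans after the last Week 12 visit.

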Statistical Analysis	
Efficacy and safety endpoints will be summarized with descriptive statistics.
 
Statistical inferential testing of the primary efficacy endpoint and key secondary endpoints will be performed while maintaining a study wide type-I error rate of two sided 5%. The primary analyses will test for a difference between the active treatment groups and placebo in Weeks 1-12, change in frequency of migraine days. The primary analyses will be based on ANCOVA model. The migraine responder rates and percentage of subjects with a migraine on the day after dosing will be tested with stratified Cochran Mantel Haenszel (CMH) tests. The same stratification factors as used in randomization will be used to perform these tests. Repeated measures will be used to test for the reduction in migraine prevalence from baseline to Week 4.
 
The migraine days reported during the initial 28-days of screening will be used as baseline. Following treatment, migraine data will be summarized and analyzed in 28 day intervals (e.g. Weeks 1-4, 5-8, 9-12). The change from baseline in migraine days for a given 4-week interval will be the difference between migraine days in that interval and the migraine days during baseline. The Week 1-12 change from baseline measure, for a subject, will be the average of the change from baseline results from each of the three intervals.
 
A 75% responder, for a given 4-week interval, will be a subject with a $\geq 75\%$ reduction in migraine days during that interval. A 75% responder over Weeks 1-12 will be a subject who achieves average reduction of $\geq 75\%$ over this time period based upon the Week 1-12 change from baseline measure. Subjects who do not complete their eDiary will have their missing data imputed.

Pharmacokinetic Analysis	
The concentrations of ALD403 will be measured in plasma from all ALD403 treated subjects using a validated assay method.
 
The PK analysis of plasma will include determination of the free ALD403 concentrations at the following times: Day 0 (within 1 hour before dosing), immediately post-dose (within 15 minutes of end of infusion), Weeks 2, 4, 8, 12 (within 1 hour before dosing), 24, and 32.

For subjects receiving placebo, selected samples will be analysed.

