8. SELECTION AND WITHDRAWAL OF SUBJECTS

8.1. Inclusion Criteria

A subject must meet all of the following criteria during the screening period and on Day 0 to be eligible for inclusion in the trial:

1. Willing and able to read, understand, and sign the Informed Consent Form (ICF) and Assent Form for the clinical trial approved by the Investigator's local Review Board or a central Institutional Review Board (IRB) or Ethics Committee (EC).
2. Has adequate venous access for administration of investigational product and collection of blood samples.
3. Male or female 18-65 years of age, inclusive, at time of informed consent.
4. Diagnosis of migraine at \leq 50 years of age with history of chronic migraine \geq 1 year prior to screening.
5. Prescription or over-the-counter medication for acute and/or prophylactic treatment of migraine has been prescribed or recommended by a healthcare professional.
6. During the 28 day screening period, must have \geq 15 to \leq 26 headache days, of which \geq 8 days were assessed as migraine days as documented in the eDiary (ICHD-III beta version, 2013 Section 1.3⁴).
7. Women of child-bearing potential, and males with partners of child-bearing potential, must agree to use adequate contraception for the duration of the study (from screening through Week 32) and for 6 months after the last dose of study drug. The following types of contraception are considered adequate provided they are locally authorized for use: oral, transdermal, or injectable (depot) estrogen and/or progestogen, selective estrogen receptor modulator therapy, intrauterine contraceptive device, double barrier method (e.g., condom and diaphragm or spermicidal gel) or vasectomy. Non-childbearing potential is defined as post-menopausal for at least 1 year, or surgical sterilization or hysterectomy at least 3 months before screening.
8. Any hormonal therapy (e.g., contraceptives, hormone replacement therapy) use is stable and ongoing for at least 3 months prior to screening.

9. Willing, committed, and able to comply with scheduled clinic visits and complete all trial-related procedures.
10. Headache eDiary was completed on at least 24 of the 28 days prior to randomization.
11. Any prophylactic use of medications for headaches must be stable for at least 3 months prior to screening.

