10.2.11.4. Pharmacokinetic and Immunogenicity Sampling

Blood samples will be collected for the analysis of plasma PK of ALD403 and for determination of anti-ALD403 antibodies in serum (immunogenicity) at specified time points in the Schedule of Events and Assessment in Section 2. All samples will be initially processed, stored, and shipped as specified in the Laboratory Manual.

10.3. eDiary Completion and Compliance Review

The subject will be instructed to complete an electronic diary (eDiary) daily from screening through Week 24.

The eDiary will be distributed to each subject at the screening visit after subject training on eDiary use by site staff. The day of eDiary distribution will start the 28 day eDiary screening

period. The subject will record information daily regarding headache characteristics, severity, and length. During the screening period, an eDiary Eligibility Report will summarize baseline headache and migraine days and eDiary compliance. The headache and compliance data from the eDiary will also be made available to the clinical site for review on a regular basis via the eDiary system portal.

Subject eligibility will be confirmed prior to randomization. Any subject found to be ineligible for the study during the screening period or prior to randomization or dosing will not be randomized or dosed.

Site staff will monitor each subjects eDiary compliance on an ongoing basis through Week 24, and will counsel subjects as needed on the on the importance of completing the eDiary daily. All follow-up with subjects regarding eDiary compliance should be documented in the source records.

During the Week 24 visit, or Early Termination visit if subject discontinues prior to Week 24, eDiary closeout must be performed while the subject is on site.

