subjects record if they took acute migraine medication on that day. In addition to the evening report the eDiary captures headaches as individual events with a start and end time. It is these headache reports which are used to derive the migraine and headache endpoints. Subjects are allowed to tell the eDiary about headaches that started today and yesterday and are unable to record headaches that started before yesterday. Headaches must be entered in order and at the completion of the headache the subject answers questions about the headache that allow the headache to be classified as a migraine or non-migraine headache as outlined in Section 2.2.2. The eDiary data from the 28 days following screening visit will be used to determine eligibility criteria, and the baseline migraine and headache results.

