3.2. Definition of Baseline

Baseline assessment for migraine and headache endpoints will be based upon the data recorded in the headache eDiary during the 28 days following screening. For other variables, the baseline assessment will be the latest available valid measurement taken prior to the administration of Investigational Product. This will generally be Day 0.

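### SAP 2.4 and Table 4 start the eDiary baseline at the first diary entry instead of at screening, so a late first entry can put up to 4 post-infusion days into baseline

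*SAP*

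**What the plan says.** The documents give two starting points for the same baseline.

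- **First diary entry.** SAP 2.4 (text): "For these data baseline is defined as the 28 days starting on the day of the first diary entry". SAP Table 4, baseline row, which covers all eDiary endpoints: "The 28 days starting from the first eDiary entry".
- **Screening.** SAP 2.2.1: "The eDiary data from the 28 days following screening visit will be used to determine eligibility criteria, and the baseline migraine and headache results". SAP 3.2 relies on "data recorded in the headache eDiary during the 28 days following screening". The protocol synopsis says: "The migraine days reported during the initial 28-days of screening will be used as baseline". Protocol 12.1.1 and 13.3.1 agree with it.

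Protocol 10.3 fixes the start of the screening window: "The day of eDiary distribution will start the 28 day eDiary screening" period. Subjects are told to complete the diary daily from screening, but inclusion criterion 10 tolerates gaps: "Headache eDiary was completed on at least 24 of the 28 days prior to randomization". Nothing requires the tolerated gaps to fall after the first entry.

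Randomisation is 28 to 30 days after the screening visit (Protocol 8.3.2), and Day 0 is 0 to 8 days after randomisation (SAP 1.2). Table 4 starts Weeks 1-4 on Day 0, the day of first treatment. No text cuts the baseline window off at Day 0. SAP Section 4 lists two deviations from the protocol, and the baseline start is not one of them.

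**The concern.** Table 4 is the table that SAP 2.4 uses to collapse daily diary data into intervals, so a programmer would probably follow it. A late first entry then moves the whole 28-day window later. If dosing follows soon after randomisation, the end of that window runs past the first infusion, and the same days are counted in both baseline and Weeks 1-4.

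This baseline is subtracted in the primary change score, is the continuous covariate in the primary ANCOVA (SAP 2.5.1), and is the denominator of each 50% and 75% responder definition (SAP 2.2.2). In affected subjects it would contain on-treatment data and so depend on the assigned arm. Even without overlap, two readers of the SAP could derive different baselines for the same subject, and that choice should be settled before unblinding.

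**Working it through.** **Notation.** S is the day of diary distribution at the screening visit. The first entry is on S+k. The first infusion is on S+28+d.

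**Overlap under Table 4.** Baseline runs from S+k to S+k+27. Days on or after the infusion = max(0, (S+k+27) − (S+28+d) + 1) = max(0, k − d).

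| First entry | d=0 | d=1 | d=2 | d=3 | d≥4 |
|---|---|---|---|---|---|
| S | 0 | 0 | 0 | 0 | 0 |
| S+1 | 1 | 0 | 0 | 0 | 0 |
| S+2 | 2 | 1 | 0 | 0 | 0 |
| S+3 | 3 | 2 | 1 | 0 | 0 |
| S+4 | 4 | 3 | 2 | 1 | 0 |

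**Why 4 is the maximum.** A subject who misses S to S+3 and completes S+4 to S+27 has 24 of 28 days and is eligible. Randomised and dosed on S+28, this subject has a Table 4 baseline of S+4 to S+31. The last four of those days are trial Days 0 to 3.

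For later randomisation, the result depends on how inclusion criterion 10 is read:
- Fixed window S to S+27: the maximum is 4, 3 or 2 days for randomisation on S+28, S+29 or S+30.
- The 28 days immediately before randomisation: the latest eligible first entry moves to S+5 or S+6 for randomisation on S+29 or S+30, and the maximum stays at 4.

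A count of 5 needs the screening period to run from S+1 to S+28. Protocol 10.3 starts it on the distribution day, and Protocol 10.2.1 requires it to be complete before randomisation, so 5 is not supported.

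**Plan's own figure.** With 350 per group, a 1-day effect and SD 4 (SAP 1.5), the standard error is 4 × √(2/350) = 0.302 day. Power is Φ(1/0.302 − 1.96) = 0.911, which reproduces the stated 90% or more.

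**Effect on the primary estimate.** Assume the planned effect of 1 day per 28 is spread evenly over days.
- Baseline lowered on active relative to placebo, maximally affected subject: 4 × 1/28 = 0.143 day.
- Average if 5% are affected: 0.05 × 0.143 = 0.007 day. If 20% are affected: 0.20 × 0.143 = 0.029 day. These shares are assumed; the documents give none.
- Relative to the standard error: 0.007/0.302 = 2% and 0.029/0.302 = 9%.
- After ANCOVA, a baseline difference enters the treatment estimate multiplied by b, the slope of post-baseline days on baseline days. If b is below 1 (an assumption), the bias is smaller than shown.
- The size scales with the true effect: 4 days per 28 gives 0.57 day per maximally affected subject.

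**Effect on a responder (illustration with assumed rates).** Take 16 migraine days per 28 before dosing and 0.30 per day after. With four overlapping days, the expected baseline is 24 × 16/28 + 4 × 0.30 = 14.9 instead of 16. A subject averaging 4 migraine days over Weeks 1-12 has a reduction of 12/16 = 75% with the screening baseline and is a responder. With the Table 4 baseline the reduction is 10.9/14.9 = 73%, which is not a response.

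**After re-anchoring to S to S+27.** The first infusion is never before S+28, so overlap is 0 for every permitted schedule. With 24 completed days, Missing Data Rule 1 scales by 28/24 = 1.167. If inclusion criterion 10 is read as the 28 days before randomisation on S+30, at most two of the 24 completed days (S+28 and S+29) lie outside S to S+27. At least 22 then remain, still above the 21 that Rule 1 needs.

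**The case against.** The overlap is a corner case. The diary is handed out after training at the screening visit, and a first entry on that day removes the difference altogether. SAP 3.3.7 counts a day as missing only if there was neither a diary interaction nor a headache. Four such days in a row at the start should be uncommon in subjects who need 15 to 26 headache days in 28. A footnote to SAP Table 1 prefers dosing on the day of randomisation, but the protocol says only within 8 days. A delay of 4 days or more removes the overlap for a first entry up to S+4. All of this stands, and it limits how many subjects are affected. It does not remove the contradiction.

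The SAP also has partial safeguards. CMH tests use the as-randomised strata (SAP 3.4.2), and the ANCOVA uses continuous baseline by design. A reader might infer that a calculated baseline differing from the IWRS stratum undermines the stratified tests. It does not, because the plan provides for such differences. The sensitivity analysis in SAP 2.7.3 uses a different baseline and limits overlap to one day, but its window ends on the day of the first dose and so still includes Day 0.

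A reader might also infer a larger bias. Post-dose rates of 0.30 per day on active and 0.40 on placebo would give 4 × 0.10 = 0.4 day per affected subject. Those rates imply an effect of 28 × 0.10 = 2.8 days, so the result cannot be set against the planned 1-day effect. The documents give neither rate.

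**Conclusion.** The contradiction is real, and SAP 2.4 and Table 4 are wrong as written. Under the permitted timings they let 1 to 4 post-infusion days into the main baseline and count them again in Weeks 1-4. This requires a late first entry and dosing within 3 days of randomisation.

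The expected effect on the primary result is small, as the figures above show. They rest on an even daily effect and an assumed affected share of 5-20%. The direction is towards no difference: with no drug effect, both arms' baselines are expected to shift equally, so this mechanism gives no reason to expect false positives. A reader might infer that the primary conclusion is at risk, but the documents do not support that. The case for change is a single, unambiguous baseline free of on-treatment data, and responder classifications that do not depend on when the first entry was made.

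**What to change.** - In SAP 2.4 and Table 4, define baseline as the 28 calendar days from eDiary distribution at screening (S to S+27), whether or not the first days were entered. Handle missed days with Missing Data Rule 1. State the dates explicitly, so that the wording in SAP 2.2.1 and 3.2 cannot be read as starting on S+1. No baseline day can then fall on or after Day 0.
- In the baseline sensitivity analysis (SAP 2.7.3), end the 28-day window on the day before the first dose.
- Leave inclusion criterion 10 and the IWRS stratification unchanged. Criterion 10 refers to the 28 days before randomisation, so imposing S to S+27 on eligibility would need a protocol amendment, and the fix does not depend on it.

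The cost is a few lines of SAP text and a change to two derivations. No new data are needed and the protocol does not change. It should be done before unblinding.
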